Can *Lactobacillus acidophilus* decrease the risk of postmenopausal osteoporosis in women?

Short Description

Background

The current recommendations for treating bone diseases are estrogen therapy and pharmacological agents. However, those treatments increase the risk of cancers and are not prescribed for long-term use. *Lactobacillus acidophilus* in ovariectomized mice could inhibit osteoclastogenic cells and promote anti-osteoclastogenic cells.

Aim of study

This study aims to evaluate the effect of *L. acidophilus* supplementation on calcium status and bone densitometry in postmenopausal women in a randomized, double-blind placebo-controlled study.

Study design

This study has three steps; namely, **1st step** is to prepare the diet supplementation of probiotics (*L. acidophilus* 1×10^9 CFU). **2nd step** is to perform the randomized, double-blind placebo-controlled clinical trial. **3rd step** is to analyze the effects of *L. acidophilus* in postmenopausal women.

Methods & Analysis

60 women of postmenopausal osteoporosis will be recruited by following inclusion and exclusion criteria. Participants will be randomized and divided into two groups to take a capsule containing probiotics and a placebo for 12 weeks. Before and after the intervention, several parameters will be conducted, such as the bone turnover and hormones parameter in blood using ELISA, the calcium mineralization in hair sample using AAS, the bone densitometry analysis in bone using DXA.

Research Design

Study settings

This study will be conducted within two (2) years for research activity and one (1) year for the publication period. There are three steps within this study; namely, **1st step** is to prepare the sample of *L. acidophilus* as diet supplementation. Probiotic capsules will contain *L. acidophilus* 1×10^9 CFU. **2nd step** is to perform the randomized, double-blind placebo-controlled clinical trial of *L. acidophilus* supplementation for twelve weeks (Figure 1). **3rd step** is to analyze the effects of *L. acidophilus* in postmenopausal women.

[figure not shown]

Figure 1. Flow diagram of patient recruitment

Eligibility criteria (inclusion, exclusion criteria)

The inclusion and exclusion criteria are provided in figure 2. Informed consent should be obtained from all patients, and the patients will be asked to notify the researchers if medical changes occurred during the intervention.

Inclusion criteria

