
 • All female participants who accepted bone densitometry measurement • Women aged 40-55 years with an intact uterus • BMI of < 34.0 kg/m², and > 7 moderate-to-severe hot flushes daily • Women will be considered to be postmenopausal if they had had either > 12 months of spontaneous amenorrhea or > 6 months of spontaneous amenorrhea with serum follicle-stimulating hormone levels of > 40 mIU/mL
Exclusion criteria

 • Diabetes • Secondary obesity • Gastrointestinal diseases • Use of dietary supplements, including calcium, in the three months before enrollment • Pharmacotherapy of lipid disorders or hypertension in the three months before enrollment • Clinically significant acute inflammatory process • Antibiotics intake within the month before enrollment • Participation in a body mass management study • The use of drugs known to modify body mass or food intake • Abuse of alcohol, nicotine, or drugs • Hormone replacement therapy • Vegetarian diet • Use of probiotic enriched or prebiotic enriched products in the three weeks before enrollment • Consumption of products with high dietary fiber content, or consumption of more than 400 g of fermented food a day • Diagnosed osteoporosis

Figure 2. Inclusion and Exclusion criteria

Interventions or exposures

[figure not shown]

Figure 3. Diagram of the intervention period

The intervention period during this study can be seen in figure 3. The diet intervention in this experiment will be performed for 12 weeks, as Ahn et al. (2019) described. Two groups will be designated in this study. Group 1 is the placebo group that will receive a capsule that consists of the excipient. The excipient will be composed of maize starch and maltodextrins (Skrypnik et al., 2019). Group 2 is the probiotic group that will receive a diet capsule consisting of *Lactobacillus acidophilus* with a dose of 1×10^9 CFU with the excipient described by Hosseini et al. (2019). In addition, it is essential to deliver self-administration of probiotic agents orally in the morning with fasting conditions to evaluate probiotic effectiveness. Subsequently, patients will be asked to keep the diet in refrigerated condition (2-7 °C).

Primary endpoints

This study will consider the change from baseline in the frequency and severity of hot flushes as primary endpoints.

Secondary endpoints

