Meanwhile, the health-related quality of life, sleep, satisfaction with treatment, and cumulative amenorrhea and breast pain will be considered as secondary endpoints.

Sample size calculation

To calculate sample size, this study refers to the Soleimani et al. (2017) study. Using a formula suggested for clinical trials, having 25 participants in each group will be considered adequate

while considering a type I error (a) of 0.05 and type II error (b) of 0.20 (power $1 - \beta = 80\%$), with 1.61 as the SD and 1.30 as the mean distinction of CTX for markers of bone resorption and BSAP for marker of bone formation as the key variable. By assuming five dropouts in each group, the final sample size will be 30 participants in each group.

Methods assignment of interventions

Randomization will be performed using a computerized random number generator, which generated the random sequence based on simple randomization. All subjects will be identified by a trial identification number and assigned a treatment code. The researchers and participants will be blinded to the treatment code until the end of the study when data will be collected and evaluated. The groups will be decided after the completion of the data analysis.

Variable assessment

All information is containing 3 days dietary records, body composition measurement, and fasting blood samples will be collected at the beginning and end of the study. DIETA 6.0 and 5D computer program by Instytut Żywości i Żywienia, Poland will be used for analyzing 3 days averages of macronutrients and micronutrient intakes. A validated questionnaire obtains personal and demographic information. Anthropometric measurements will be measured using body composition analysis.

Biomarkers of bone turnover and hormones

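### Beyond hormone therapy, supplements and diagnosed osteoporosis, the exclusion list does not address drugs that alter bone turnover, although bone markers drive the sample size

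*Protocol*

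**What the plan says.** The drug-related exclusions in Protocol, Figure 2 are:

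- "Pharmacotherapy of lipid disorders or hypertension in the three months before enrollment"
- "The use of drugs known to modify body mass or food intake"
- antibiotics in the preceding month
- "Hormone replacement therapy"
- "Use of dietary supplements, including calcium, in the three months before enrollment"

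The same list also excludes a disease state, "Diagnosed osteoporosis". No entry names anti-resorptive drugs, bone-forming drugs or systemic glucocorticoids.

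Three other places bear on this:

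- **Background:** "The current recommendations for treating bone diseases are estrogen therapy and pharmacological agents". Of these two kinds of treatment, Figure 2 excludes only the first by name.
- **Methods & Analysis:** "60 women of postmenopausal osteoporosis will be recruited by following inclusion and exclusion criteria". This conflicts with the exclusion of diagnosed osteoporosis.
- **Sample size calculation:** the trial is sized on "CTX for markers of bone resorption and BSAP for marker of bone formation as the key variable".

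The aim is stated in terms of calcium status and bone densitometry. The named primary endpoints, however, are the frequency and severity of hot flushes, and the named secondary endpoints include no bone measure.

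**The concern.** The list restricts several drug classes, but it does not address the class closest to what the trial measures in bone: CTX, TRAP5b, BSAP, PINP and DXA. A woman without diagnosed osteoporosis who takes a drug that alters bone turnover is not clearly barred. Examples are an anti-resorptive taken for low bone mass, or a systemic glucocorticoid taken for another condition.

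If such a woman's markers are largely governed by her drug, the capsule may have less room to move them. The average between-group difference then shrinks. At stake is precision on the bone variables, in a design that has no spare power on its key variable. A statistical analysis plan cannot repair this, because it cannot change who was enrolled.

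**Working it through.** **Inputs from the protocol (Sample size calculation).** SD 1.61; mean difference 1.30; type I error 0.05; power 80%; 25 evaluable per group; 5 dropouts per group, giving 30. Sidedness is not stated; the two-sided formula returns the protocol's 25, whereas a one-sided test gives 19.

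**Step 1: reproduce the plan's figure.** The standardised difference is d = 1.30 / 1.61 = 0.807. The normal-approximation formula gives

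n = 2 × (1.96 + 0.842)² / 0.807² ≈ 24.1, rounded up to 25 per group.

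Adding 5 dropouts gives 30. The stated size is reproduced. A two-sample t-test at 25 per group has 79.9% power.

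**Step 2: dilution.** The protocol gives no share of women on bone-active drugs. Assume that a share p shows no response to the capsule and that the SD stays at 1.61. The mean difference becomes 1.30 × (1 − p). Two-sided t-test results:

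| Assumed p | Mean difference | Power at 25 per group | n per group for 80% power |
|---|---|---|---|
| 0% | 1.300 | 79.9% | 25.1 |
| 2% | 1.274 | 78.3% | 26.1 |
| 5% | 1.235 | 75.7% | 27.7 |
| 10% | 1.170 | 71.1% | 30.7 |
| 20% | 1.040 | 61.0% | 38.6 |

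In a sample of 60, p = 5% is 3 women and p = 10% is 6. At p = 10% the required number is above 30 per group, so the planned enrolment would fall just short of 80% power even with no dropout.

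**Step 3: which rows are plausible.** This depends on which population statement governs.

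- *Figure 2 governs.* Diagnosed osteoporosis is excluded, which removes the usual reason for taking anti-osteoporosis drugs, and the age range is 40 to 55 years. The remaining users are women without that diagnosis, so the low rows (2% to 5%) are the natural reading.
- *Methods & Analysis governs.* Women with osteoporosis are recruited, the safeguard is gone, and the higher rows become relevant.

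**Step 4: the other mechanism, added variance.** Suppose the drugs only shift the marker level by k SD in 10% of women. The variance is then multiplied by 1 + 0.10 × 0.90 × k². That is 1.09 for k = 1 (power 76.4%) and 1.36 for k = 2 (power 67.0%). This applies to an unadjusted comparison of end-of-study levels. The protocol takes fasting blood at the beginning and end, so under stable drug use the shift cancels in change from baseline. I do not rely on this scenario.

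**The case against.** The strongest reply is that the main route is already closed. Figure 2 excludes hormone therapy, calcium and other supplements, and diagnosed osteoporosis. A reader might infer that drugs acting on bone are simply not excluded. The list does not support that: hormone therapy, one of the two bone treatments named in the background, is there by name. What remains uncovered is a narrower group. Some glucocorticoid users might also be caught by the exclusion of drugs that modify body mass or food intake, although the text does not say so.

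A reader might also infer that entry of such women would hide a real effect or bias the comparison. The documents do not support that either. Allocation is random, so no bias is expected. Simple randomisation of 60 women can leave users unevenly split, but the standard error already allows for chance imbalance, so it is not a further harm. Zero response in every user is an assumption, and anti-resorptive drugs, bone-forming drugs and glucocorticoids do not all act on turnover in the same direction.

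Finally, the named primary endpoints are hot flushes, so the power loss concerns variables that the protocol uses for sizing but does not list as endpoints. That is correct and limits the weight of the point.

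What does not stand is relying on the osteoporosis exclusion alone. It is a criterion on diagnosis rather than on drugs, and the protocol contradicts it elsewhere.

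**Conclusion.** The gap is real but modest. As written, women without diagnosed osteoporosis who take drugs that alter bone turnover can enrol. The consequence is possible dilution on the bone variables, not expected bias.

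If Figure 2 defines the population, the loss is probably about 2 to 4 percentage points of power on CTX/BSAP (79.9% to 78.3% at p = 2%, or to 75.7% at p = 5%). It would be about 9 points at p = 10%. If the conflict is resolved toward women with osteoporosis, the share of users, and with it the loss, could be larger.

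These sizes rest on an assumed share of users, no response in any of them, an unchanged SD and 25 evaluable women per group. The documents supply neither the share nor the response among users, so the figures show sensitivity and are not estimates.

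**What to change.** Add one exclusion to Figure 2: current or recent use of drugs known to alter bone turnover. The investigator should set the drug list and the look-back period. The criterion should say that women taking such drugs are not enrolled and that no treatment is stopped for the trial.

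In the same revision, reconcile the recruitment of women with postmenopausal osteoporosis (Methods & Analysis) with the exclusion of diagnosed osteoporosis (Figure 2), because that decision determines how much the new criterion matters.

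The cost is one line in Figure 2 and one screening question. The downside is that a few otherwise eligible women are not enrolled.

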This study will analyze the biomarkers of bone turnover and hormones as described by Villareal et al. (2016). Briefly, venous blood samples will be obtained after fasting overnight and analyzed in the laboratory. Enzyme-linked immunosorbent assay (ELISA) will be used to measure C-terminal telopeptide of type I collagen (CTX) and tartrate-resistant acid phosphatase isoform-5b (TRAP5b) as markers of bone resorption and bone-specific alkaline phosphatase (BSAP) as a marker of bone formation. Radioimmunoassay will be used to measure N-terminal propeptide of type I procollagen (PINP) as an additional marker of bone formation. ELISA is also used to measure high-molecular-weight adiponectin and insulin-like growth factor-1. Chemiluminescent immunoassays will be used to measure parathyroid hormone (PTH) and cortisol.

Hair sample

A hair strand of 1 cm of length is collected from the occipital region. The sample will be taken by a member of the study team shortly after the hair had been washed with a shampoo not containing functional components. Each woman is instructed on how to wash her hair. Moreover, it will be clearly explained to patients that reliable results could be obtained only by complying with this procedure. Hair spray or hair dye is forbidden during the study (Skrypnik et al., 2019).

Calcium analysis

The calcium contents of the hair and serum will be determined after digestion in 65% (w/w) spectra pure HNO₃ using a Microwave Digestion System. Upon digestion and dilution with deionized water, the concentrations in the mineral solutions are measured using flame atomic absorption spectrometry (Skrypnik et al., 2019).

Bone densitometry analysis

This analysis will be conducted in the accredited laboratory in Poznan, Poland. Subsequently, the subjects are asked to undergo bone mineral densitometry using a DEXA scan. The scan will be performed on a Hologic DXA scan machine.

Products used in the research

1. A capsule consists of Maize starch and maltodextrins for the Placebo Group.
2. A capsule contains *Lactobacillus acidophilus* with a dose of 1×10^9 CFU for the Probiotic Group.

Ascertainment Feasibility

The study will be conducted in the Department of Obesity and Metabolic Disorders Treatment and Clinical Dietetics, Karol Marcinkowski University of Medical Sciences (PUMS), Poznan, Poland. This place receives patients who meet the inclusion criteria described above.

Techniques and actual available equipment

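### No declared endpoint is a bone or calcium outcome, although the aim is calcium status and bone densitometry and the sample size rests on CTX and BSAP

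*Protocol*

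**What the plan says.** Four parts of the protocol bear on what the trial tests.

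- **Title and aim.** The title asks whether the probiotic can "decrease the risk of postmenopausal osteoporosis in women". The Aim of study is to evaluate its "supplementation on calcium status and bone densitometry in postmenopausal women in a randomized, double-blind placebo-controlled study".
- **Primary endpoints.** "This study will consider the change from baseline in the frequency and severity of hot flushes as primary endpoints".
- **Secondary endpoints.** The section states that "the health-related quality of life, sleep, satisfaction with treatment, and cumulative amenorrhea and breast pain will be considered as secondary endpoints".
- **Sample size calculation.** 25 per group, raised to 30 for dropout, with type I error 0.05, power 80%, an SD of 1.61 and "1.30 as the mean distinction of CTX for markers of bone resorption and BSAP for marker of bone formation as the key variable".

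The measurements described match the aim. Methods & Analysis lists bone-turnover and hormone parameters in blood before and after treatment, followed by "the calcium mineralization in hair sample using AAS, the bone densitometry analysis in bone using DXA". The Biomarkers section names CTX, TRAP5b, BSAP and PINP. The Calcium analysis section adds serum: "The calcium contents of the hair and serum will be determined after digestion". The inclusion criteria in Figure 2 require more than 7 moderate-to-severe hot flushes a day, which fits the declared primary endpoints but not the aim.

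**The concern.** The aim, the declared endpoints and the sample-size basis name three different targets: calcium and densitometry, hot flushes, and bone-turnover markers. All three are stated outright, so this is a conflict within the text and not a detail left for a later document.

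If the plan is followed literally, the trial's formal conclusion rests on hot flushes and does not answer its title or aim. The results that would answer them have no endpoint status. If the report emphasises one of them, the protocol does not show that it was the outcome chosen in advance. The stated 80% power would also be read as belonging to the primary endpoints, and it does not.

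**Working it through.** **1. Which outcomes are endpoints?**

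- Named endpoints: hot-flush frequency and severity (2 primary); quality of life, sleep, satisfaction with treatment, cumulative amenorrhea and breast pain (5 secondary, counting the last two separately). Total 2 + 5 = 7, of which 0 are bone or calcium outcomes.
- Planned bone or calcium outcomes: CTX, TRAP5b, BSAP, PINP, hair calcium, serum calcium and DXA. Total 4 + 2 + 1 = 7, of which 0 are named endpoints. PTH is left out of this count; including it gives 0 of 8.

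**2. Reproducing the sample size.** Inputs from Sample size calculation: difference 1.30, SD 1.61, type I error 0.05, power 0.80. Sidedness is not stated.

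- Standardised difference: 1.30/1.61 = 0.807 SD.
- Formula: n per group = 2 × ((z for alpha + z for power)/0.807)².
- Two-sided: 2 × ((1.960 + 0.842)/0.807)² = 24.1, rounded up to 25. This is the plan's figure.
- One-sided: 2 × ((1.645 + 0.842)/0.807)² = 19.0. This does not match, so two-sided is assumed from here on.
- Power of a two-sample t-test for 0.807 SD at 25 per group: 79.9%.
- Dropout: 25 + 5 = 30 per group, 60 in total, as stated.

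The calculation is correct for whatever variable has a difference of 1.30 and an SD of 1.61.

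**3. Which variable is that?** The sentence attaches the pair to CTX and BSAP together. It gives no units and does not say whether the figures are changes or end values. One difference and one SD cannot be assumed to describe both a resorption and a formation marker. The choice matters: if both were primary with alpha split to 0.025 each, and the same pair held for both (an assumption), the same formula gives 2 × ((2.241 + 0.842)/0.807)² = 29.2, so 30 evaluable per group instead of 25.

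**4. What does 25 per group mean for another outcome?** For any other continuous outcome, only a standardised statement is possible. By unadjusted t-test at two-sided 0.05, 80% power is reached at 0.81 SD of the analysed variable with 25 per group, and at 0.74 SD with 30 per group. The protocol gives no difference or SD for hot flushes, calcium or DXA, so no sample size can be computed for them. As an illustration over an assumed range of effects, t-test power with 25 per group is 18% at 0.3 SD, 41% at 0.5 SD and 79% at 0.8 SD.

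**5. Are the declared primary endpoints measured?** The shown text describes dietary records, body composition, blood markers, hair and serum calcium, and DXA. It describes no hot-flush diary or severity scale, and no instrument for quality of life, sleep or satisfaction. The only questionnaire mentioned collects personal and demographic data. Figure 3, the intervention diagram, is not shown and might list such assessments.

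**The case against.** The best defence is that the intention is plain from everything except the two endpoint sections. The title, the aim, the measurements and the sample size all concern bone, and calling CTX and BSAP the key variable gives them some priority. That is fair as a guess at intent. It does not cure the text, because the Primary endpoints section is explicit and a later analysis plan would not normally replace a primary endpoint that the protocol states. Nor does the key-variable wording agree fully with the aim, which names calcium and densitometry and not bone turnover.

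Some stronger readings are tempting, but the protocol does not support them.

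- *All declared endpoints are menopausal symptoms.* Quality of life and satisfaction with treatment are not. The accurate statement is that none is a bone or calcium outcome.
- *The trial is sized on CTX.* The sentence names CTX and BSAP together and does not say which one the figures describe.
- *Endpoints could be chosen after sight of coded comparisons.* A reader might infer this from "The groups will be decided after the completion of the data analysis". Beside the blinding sentence, that can equally mean that codes are revealed after the analysis, which is ordinarily a safeguard. The protocol describes no such choice, and the point does not depend on it.
- *Hot flushes are not measured at all.* The shown text describes no method, but a figure is missing, so this cannot be asserted.

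**Conclusion.** The point holds and must be fixed. The aim, primary endpoints and sample-size basis disagree, and no other part of the protocol reconciles them. None of the 7 named endpoints is a bone or calcium outcome, and none of the 7 planned bone or calcium outcomes is a named endpoint. The 80% power does not extend to the declared primary endpoints.

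This is not an arithmetic error: 25 and 30 per group both reproduce. Nor is it shown that the trial is too small. Whether 30 per group is enough for calcium or DXA is unknown until a worthwhile difference and an SD are stated. The figures rest on a two-sided 0.05 test (inferred from the reproduced number), a continuous outcome and an unadjusted comparison. The mismatch itself rests on no assumption.

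**What to change.** Before any outcome data are examined, amend the protocol so that the aim, primary endpoint and sample-size basis name the same target.

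1. In Primary endpoints, replace hot flushes with one named, already-planned outcome, defined as the between-group difference in change from baseline to week 12. Under the aim as written, the candidates are hair calcium, serum calcium or a DXA measure. One of CTX or BSAP is also possible, with bone turnover then named in the aim.
2. If CTX or BSAP is chosen, state which marker 1.30 and 1.61 describe, in what units, and whether they are changes or end values. If the pair describes the chosen marker, the 25 per group stands for that one marker.
3. If calcium or DXA is chosen, withdraw the 80% power statement based on 1.30 and 1.61. State instead the difference detectable with 25 per group: about 0.81 SD of the analysed variable by unadjusted t-test, expressed in that outcome's units.
4. List the other bone and calcium outcomes as secondary. Keep hot flushes and the other symptom and patient-reported outcomes below the primary; whether as secondary or exploratory is the sponsor's choice.
5. Reconcile the hot-flush entry criterion with the aim.

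If a hot-flush objective is really intended, change the title, aim and sample-size basis instead, and specify how hot-flush frequency and severity are measured.

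The cost is a substantive amendment, because the primary hypothesis changes, and possibly a less favourable power statement. The bone or calcium route needs no new procedures, as those measurements are already planned before and after treatment. The hot-flush route needs a new sizing basis and, unless Figure 3 already provides one, a described measurement method.

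### The 80% power claim supports one test of one bone marker, while the protocol declares two unranked hot-flush primary endpoints

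*Protocol*

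**What the plan says.** The Primary endpoints section reads: "This study will consider the change from baseline in the frequency and severity of hot flushes as primary endpoints". The noun is plural. The section does not rank frequency and severity, combine them, or say whether one or both must succeed.

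The Secondary endpoints section lists quality of life, sleep, treatment satisfaction, amenorrhea and breast pain. Neither CTX nor BSAP appears in either endpoint section.

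The Sample size calculation section makes one calculation, with "type I error (a) of 0.05" and "type II error (b) of 0.20". Its inputs are given "with 1.61 as the SD and 1.30 as the mean distinction of CTX", and the sentence continues with "CTX for markers of bone resorption and BSAP for marker of bone formation as the key variable". So two markers are called one variable and share one SD and one difference. The result is "having 25 participants in each group will be considered adequate", raised to 30 per group for five dropouts in each. Hot flushes do not enter this calculation.

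**The concern.** The protocol names a pair of variables in two places: frequency and severity as primary endpoints, CTX and BSAP as the basis of the sample size. The arithmetic is that of a single test, and it concerns variables that are not endpoints. A reader cannot tell which test the 80% belongs to.

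Two things are at stake. First, the power claim does not attach to the declared primary endpoints, and it would be too high if both members of a pair had to succeed. Second, with two equal primaries and no stated rule, a significant result on either one could be presented as a success at 5% although two chances had been taken.

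**Working it through.** **Inputs from the protocol (Sample size calculation).** Type I error 0.05, power 80%, SD 1.61, difference 1.30, 25 evaluable per group, 5 dropouts per group. Sidedness is not stated.

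**Inputs assumed.** The correlation between the two test statistics is not given; 0 to 0.9 is shown. Where two tests are considered, each variable is assumed to have the protocol's one effect size. For hot flushes nothing in the document supports that assumption, so the power figures below speak directly only to the CTX/BSAP pair.

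**1. Reproduce the plan's figure.**
- Standardised difference: 1.30 / 1.61 = 0.807.
- Normal approximation, two-sided 0.05: n = 2 × [1.61 × (1.960 + 0.842) / 1.30]² = 24.08, rounded up to 25 per group. This matches.
- One-sided 0.05 gives 18.97, rounded up to 19, which does not match.
- Two-sample t-test power at 25 per group, two-sided 0.05: 79.9%.
- Dropout: 25 / (1 − 5/30) = 30 per group, as stated.

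So 25 per group is right for one two-sided test of one variable.

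**2. Both variables must succeed, each at 0.05 with 80% power.** Joint power is P(Z₁ < 0.842 and Z₂ < 0.842) for a bivariate normal with correlation ρ. At ρ = 0 it is 0.80 × 0.80 = 0.64.

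| ρ | Joint power |
|---|---|
| 0 | 64% |
| 0.5 | 69% |
| 0.7 | 71% |

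Starting from the normal-approximation power of 81.5% at 25 per group instead of 80%, the figures are 66%, 71% and 73%. Reaching 80% joint power by that approximation needs 32 evaluable per group at ρ = 0, 31 at 0.5 and 29 at 0.7.

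**3. Either variable may succeed, each tested unadjusted at 0.05.** Family-wise error is 1 − P(|Z₁| < 1.96 and |Z₂| < 1.96). At ρ = 0 it is 1 − 0.95² = 0.0975.

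| ρ | Family-wise error |
|---|---|
| 0 | 9.75% |
| 0.5 | 9.07% |
| 0.8 | 7.81% |
| 0.9 | 7.04% |

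This calculation needs no effect size, so it applies to any pair, including frequency and severity.

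**4. Either may succeed, with a Bonferroni split (0.025 each).** Family-wise error is at most 5%. The t-test power per variable at 25 per group is 70.5%. The chance that at least one succeeds is 1 − P(both miss); at ρ = 0 this is 1 − 0.295² = 0.913.

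| ρ | Power for at least one |
|---|---|
| 0 | 91% |
| 0.5 | 85% |
| 0.7 | 81% |
| 0.8 | 79% |

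**5. Fixed sequence.** The first-ranked variable keeps 0.05 and 79.9% power at 25 per group, and family-wise error stays at 5%. If CTX is ranked first and the 1.30 and 1.61 apply to it, the stated figures hold for CTX.

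**The case against.** A reader might infer that the two primary endpoints share the 0.05/80% calculation, and that either the error rate or the power must therefore fail. The document does not support this, for three reasons.

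- The hot-flush endpoints have no part in the calculation. They have no stated effect, SD or power.
- The protocol states no either-may-succeed rule and no unadjusted testing. The 7% to 10% error describes a rule that it does not contain. An order or an alpha split is commonly left to the analysis plan, which may exist and is not shown, so its absence is not an error in itself.
- Two rules would keep both figures. A fixed sequence keeps 0.05 and 80% for the first variable. A Bonferroni split at 25 per group keeps error at 5% and at-least-one power at 81% to 91% for correlations 0 to 0.7, if both variables have the assumed effect. The 70.5% is power per test, which is not the measure of success under an either-may-succeed rule.

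It can also be said that calling CTX and BSAP one key variable is loose wording for a single sizing variable, and that no 5% claim attaches to markers that are not endpoints.

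All of this stands, and it limits the point. It does not remove what the protocol itself fixes. The stated power belongs to a variable that is not an endpoint, the declared primaries are two and unranked, and the 25 per group fits one test. An analysis plan can set a testing order; it cannot make a bone-marker calculation into one for hot flushes.

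**Conclusion.** The point holds in a limited form. The calculation is arithmetically correct for one two-sided test of one variable (t-test power 79.9% at 25 per group). The stated 80% applies to neither hot-flush endpoint. It also does not apply to a requirement that both CTX and BSAP succeed, where joint power is about 64% to 71% for correlations 0 to 0.7. Those figures assume the correlation and assume that each marker has 80% power.

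The family-wise error of about 7% to 10% (correlation 0.9 to 0) is conditional: it arises only if either of two equal primaries may succeed unadjusted at 0.05. The basic fault is that the sample size is not tied to a named primary endpoint. The missing rank order adds to it, because it leaves open which result the trial is meant to stand on. This should be corrected.

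**What to change.** In the Primary endpoints section, name one primary endpoint and make it the variable on which the sample size is calculated. CTX change at week 12 is an example that fits the study's bone aim. Make the second variable (then BSAP) the first secondary endpoint, tested at 0.05 only if the first is significant.

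In the Sample size calculation section, state that the difference, the SD and the 80% power refer to the primary variable only.

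If hot flushes stay primary, rank frequency and severity in the same way, and state that the 80% does not apply to them unless a hot-flush effect and SD are supplied.

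The cost is one sentence in each section. With CTX first, no extra participants are needed. A new calculation for hot flushes could give a different number, which cannot be foreseen from this document. The downside of the fixed order is that the second variable supports no confirmatory claim if the first fails.
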